Cover Page for ClinicTrials.gov

Document:

IN-HOME Study Protocol and Statistical Analysis Plan

Official Study Title:

Testing Preliminary Effectiveness of a Community Health Worker (CHW) Training Program to Support African American and Latino Male Caregivers of Older Adults

Document Date:

January 1, 2023

IN-HOME feasibility evaluation

I. Original proposal narrative

The Phase 1 feasibility evaluation, a RCT with a two-group pre–post design with 87 CHWs will explore the following question: To what extent is IN-HOME exposure (treatment) associated with greater CHW knowledge, skills, and perceived self-efficacy to conduct outreach to reduce caregiver burden for African American and Latino male informal caregivers of older adults compare to CHWs reviewing caregiver information from AARP’s English “Care at Home” resource page (control)? What is the relation between demographic characteristics (e.g., age and race/ethnicity) and experimental differences in knowledge, skills, and perceived self-efficacy? What is the extent of difference in outcomes between treatment and control participants?

We will enroll 60 CHWs per arm. Eligible participants will (1) be at least 18 years old, (2) self-identify as a CHW, (3) live in the United States, (4) conduct outreach, to African American and Latino male informal caregivers, (5) have at least six months of field experience and (6) be an active CHW within the last six months.

We will randomly assign participants to the treatment and control conditions. Any stratification based on potentially confounding factors will be done by using covariates in the full analyses. Treatment participants will complete a pretest before and a posttest after viewing the IN-HOME prototype. Control participants will complete a pretest before and a posttest after reviewing caregiver information from AARP’s English “Care at Home” resource page.

IN-HOME is feasible if the treatment group shows statistically significant higher mean scores in knowledge, skills, and perceived self-efficacy at posttest compared to the control group. We will use covariate-adjusted ANCOVA to control for group differences (e.g., received caregiver training before) that may confound outcomes. We will use two-tailed tests to identify potential iatrogenic effects.

II. IN-HOME study research questions

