1. To what extent is IN-HOME exposure (treatment) associated with greater CHW knowledge, skills, and perceived self-efficacy to conduct outreach to reduce caregiver burden for African American and Latino male informal caregivers of older adults compare to CHWs reviewing caregiver information from an online resource (control)?
 - What is the relation between demographic characteristics (e.g., age and race/ethnicity) and experimental differences in knowledge, skills, and perceived self-efficacy?
2. What is the extent of difference in outcomes between treatment and control participants?
 - What is the relation between demographic characteristics (e.g., age and race/ethnicity) and experimental differences in knowledge, skills, and perceived self-efficacy?

3. To what extent do CHWs exposed to IN-HOME show greater gains in knowledge compared to the control group?
 - What is the relation between demographic characteristics (e.g., age and race/ethnicity) and experimental differences in knowledge, skills, and perceived self-efficacy?
4. To what extent do CHWs exposed to IN-HOME are more prepared to provide support to male caregivers compared to the control group?
 - What is the relation between demographic characteristics (e.g., age and race/ethnicity) and experimental differences in knowledge, skills, and perceived self-efficacy?

For specific hypotheses, see the research question and hypotheses document, located here:
S:\Projects\IN-HOME\Feasibility evaluation\Methods and analysis

III. IN-HOME study summary

Study design: Randomized controlled trial with a two-group online pretest/posttest design.

Study population and sites: The study population will include active CHWs. The study will be conducted online and include participants recruited by six CHW organizations in Alabama, Georgia, Florida, Virginia, Illinois, and Texas.

Treatment regimen: Treatment group participants will view the IN-HOME prototype. Control group participants will view materials from AARP's English "Care at Home" resource page.

Randomization: The research assistant will randomly assign participants to the control or treatment group after they consent to the study.

Institutional Review Board (IRB): KDHRC received approval for pilot testing materials on May 2, 2023 IRB # 00005850.

The final approved IRB package can be found at: S:\IRB\Reviews\Reviews - general\2023\2023-02-01 - 2023-0213 - In Home\12 - Amended approval packet

IV. Pre-launch survey review

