- Compare participant ID (last-initials-state) between pre and posttest responses.
- If the participant matches, merge the pre and posttest variables.
- Archive pretest and posttest survey files.
- Save merged survey files as _MERGED.

6. Delete observations, if applicable.
7. Clean data in preparation for data analysis.

VI. Data analysis

1. Create dichotomous variables for incorrect and correct answers
 - a. For the knowledge and skills variables, we will code correct answers as '1' and incorrect answers as '0'.
 - b. The new variable name will use “_correct” (e.g. q1_t1_correct).
2. Create a dummy variable for treatment.
 - a. For all participants in the treatment group, we will code the variable “treatment” with a '1' and control group participants with a '0'.
3. Create composite variables for the knowledge, skills, and self-efficacy questions.
 - a. Create composite variables for each participant that sums all their answers for each outcome and divides them by the total number of questions to create composite scores, ranging from 0 to 100 (e.g., a composite knowledge score of 100 means that a participant correctly answered all knowledge questions on the pretest).
 - b. The new variable names will be “know_comp_t1,” “know_comp_t2,” “att_comp_t1,” “att_comp_t2,” “se_comp_t1,” “se_comp_t2,” “int_comp_t1,” and “int_comp_t2.”
4. Create “gain” or “differences” score for the composite variables.
 - a. Subtract the t1 composite variables from the t2 composite variables to get the change in composite score from pretest to posttest for each outcome area.
 - b. The new variable names will be “know_comp_diff,” “att_comp_diff,” “se_comp_diff,” and “int_comp_diff.”

Methods

- Between groups t-tests on each outcome’s composite score at pretest and posttest.
- Within group t-tests between each outcome’s pretest and posttest composite scores.

- Regression analyses using each primary outcome's posttest composite score as the dependent variable and group assignment as the primary independent variable, while controlling for participant characteristics at baseline including race, ethnicity, age, sex, education, time as CHW, paid/volunteer status, having over 16hrs of training, number of usual topics outreach is conducted on, and whether participants had been trained previously in older adult care.

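### The pretest score is not named as a covariate in the posttest regression, and gains have no between-arm analysis: valid under randomization, but less precise than it could be

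*Combined protocol and SAP*

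**What the plan says.** Section VI, Methods, lists three analyses.

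- Between-group t-tests on each outcome's "composite score at pretest and posttest", that is, on each occasion separately.
- Within-group t-tests of pretest against posttest.
- A regression with each outcome's "posttest composite score as the dependent variable and group assignment as the primary independent variable, while controlling for participant characteristics at baseline including race". The list continues to ten items: demographics and education, length and type of CHW work, range of outreach topics, and two training items. No pretest composite is among them.

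Section I describes the adjusted analysis as follows: "We will use covariate-adjusted ANCOVA to control for group differences (e.g., received caregiver training before) that may confound outcomes". Its one example is prior training. The success rule in the same section is "IN-HOME is feasible if the treatment group shows statistically significant higher mean scores in knowledge, skills, and perceived self-efficacy at posttest", relative to control.

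Research question 3 (section II) asks: "To what extent do CHWs exposed to IN-HOME show greater gains in knowledge compared to the control group". Step 4a of section VI builds the gain scores: "Subtract the t1 composite variables from the t2 composite variables to get the change in composite score from pretest to posttest". None of the three Methods items uses them between arms. Section II also refers the reader elsewhere: "For specific hypotheses, see the research question and hypotheses document, located here". That file is not part of the public document.

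**The concern.** In a two-group pretest/posttest trial, the outcome's own pretest score is usually the strongest predictor of the posttest score. Leaving it out of the model does not bias a randomized comparison, but its share of the outcome variance stays in the error term and a chance pretest difference passes into the estimate. The success rule depends on significance, apparently for three outcomes together, so lost precision bears directly on the feasibility conclusion.

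The second gap concerns research question 3. With no between-arm analysis of gains named, the within-arm t-tests are the only listed tests of change. A significant change in one arm and not in the other is not evidence of a treatment effect, and the plan should not leave that as the nearest available answer.

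**Working it through.** **Inputs from the document.** Arms of 52 control and 55 treatment, total 107 (Data collection); two-tailed tests (section I); pretest and posttest linked by participant ID (Data cleaning). The planned 60 per arm cannot be reproduced, because no effect size, SD, alpha or power accompanies it.

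**Assumed.** Alpha 0.05; effect d = 0.4 SD; equal SDs at both occasions; pre-post correlation r from 0.2 to 0.7.

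**Formulas, no other covariates.** The SE of a posttest difference is √(1/52 + 1/55) = 0.193 SD. Relative to posttest only, the variance of the treatment estimate is 1 − r² with the pretest as covariate and 2(1 − r) for a t-test on gain scores. Power is from the noncentral t with noncentrality d / (0.193 × √variance ratio), and 105 df without or 104 df with the pretest. Posttest only: 0.4/0.193 = 2.07, power 54%. The equivalent N is 107/(1 − r²).

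| r | variance ratio, pretest as covariate | power, pretest as covariate | equivalent N | variance ratio, gain score | power, gain score |
|---|---|---|---|---|---|
| 0.2 | 0.96 | 55% | 111 | 1.6 | 37% |
| 0.3 | 0.91 | 57% | 118 | 1.4 | 41% |
| 0.4 | 0.84 | 61% | 127 | 1.2 | 46% |
| 0.5 | 0.75 | 66% | 143 | 1.0 | 54% |
| 0.6 | 0.64 | 73% | 167 | 0.8 | 63% |
| 0.7 | 0.51 | 82% | 210 | 0.6 | 75% |

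The SE falls by 1 − √(1 − r²), which is 2% at r=0.2 and 29% at r=0.7. At d=0.3, power goes from 34% to 35%, 43% and 58% at r = 0.2, 0.5 and 0.7. At d=0.5 it goes from 73% to 74%, 84% and 95%.

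**With the ten covariates in the model.** This is the regression the plan describes. Let the covariates explain a share R of both scores, with overall r held fixed. If the same combination of covariates drives both, the correlation left for the pretest to use is (r − R)/(1 − R). At r=0.5 and R=0.3 it is 0.2/0.7 = 0.29, so the variance falls by only 0.29² ≈ 8%. At r=0.3 and R=0.3 it is zero. A simulation (d=0.4, 4,000 replicates, Monte Carlo SE about 0.8 points) gave the following power without / with the pretest:

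| R | r=0.3 | r=0.5 | r=0.6 |
|---|---|---|---|
| 0 | 47.8 / 50.9 | 49.2 / 59.6 | 48.6 / 65.8 |
| 0.1 | 53.2 / 55.0 | 54.1 / 62.6 | 53.8 / 69.4 |
| 0.2 | 58.7 / 58.8 | 57.2 / 63.8 | 58.6 / 69.8 |
| 0.3 | 64.0 / 63.3 | 65.4 / 68.0 | 64.4 / 71.8 |

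At R=0 the starting power is below 54% because ten uninformative covariates cost precision.

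**All three outcomes significant (d=0.4 on each, no other covariates).** If the tests were independent, power would be 0.536³ = 15% without the pretest and 0.658³ = 28% with it at r=0.5. If they correlate at 0.7, the figures are 34% and 48%.

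**Chance imbalance.** The pretest difference between arms also has SE 0.193 SD, so it exceeds 0.2 SD in either direction in about 30% of randomizations (0.2/0.193 = 1.03 SE). A one-SE imbalance moves the unadjusted estimate by r × 0.193: 0.04 SD at r=0.2 and 0.14 SD at r=0.7, averaging zero over randomizations.

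**Validity.** In 6,000 simulated trials per setting (r = 0.5 and 0.7), the posttest-only estimate averaged 0.50 for a true 0.5, with type I error of 5.0% to 5.2%.

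**Within-arm tests.** With equal true gains in both arms and r = 0.5 to 0.6, the two within-arm verdicts disagree in 44% to 50% of trials at gains of 0.25 to 0.3 SD, 19% to 30% at 0.4 SD, and 2% or less at 0.6 SD.

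**The case against.** The strongest reply is that the pretest may be intended. The covariate list is introduced by an open word, section I uses the term ANCOVA with only an example, the pretest composites are built and merged, and the specific hypotheses are in a file not seen here. This stands as a limit: the finding is that the pretest is not named, not that it will be left out. But a list detailed enough to include the number of outreach topics should not leave the outcome's own baseline to inference.

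The second reply is that the larger power figures compare against a model with no covariates. That comparator fits the planned posttest t-test. For the planned regression, the second table applies, and there the benefit runs from none to moderate. This also stands.

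Third, every input to the size is assumed, and 52/55 may not be the analysed numbers: 123 consented, 123 − 107 = 16 are not shown by arm, and ID matching and possible deletions follow. The same gap means that the claim of no bias depends on the analysed participants preserving randomization.

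Fourth, the plan nowhere says it will infer an effect from differing within-arm results; its success rule is between arms. The disagreement rates are therefore a caution, not a fault in the stated rule.

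**Conclusion.** The point holds as an avoidable loss of precision, not a validity failure. The plan names no pretest covariate and no between-arm analysis of gains. Provided the analysed set preserves randomization, the posttest comparison is unbiased and can also answer research question 3, but the plan does not say that it is meant to. At an assumed 0.4 SD effect with 52 and 55 analysed, the benefit in the planned regression is 10 points of power falling to 3 at r=0.5, 17 falling to 7 at r=0.6, and 3 falling to none at r=0.3, as the covariates explain 0 to 30% of both scores. Against the unadjusted t-test it is 1 to 28 points over r = 0.2 to 0.7 (54% to between 55% and 82%). The true size depends on a correlation the documents do not give. The remedy costs very little even at the low end, so it should be made.

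**What to change.** - Add each outcome's own pretest composite to its posttest regression: know_comp_t1 for knowledge, se_comp_t1 for self-efficacy, and the skills pretest composite for skills. Step 3 of section VI calls for a skills composite, but step 3b gives it no variable name, so name the two skills variables first.
- State that the treatment coefficient from this model, with its 95% interval, is the estimate for research questions 1 to 3 and for the feasibility criterion. With the pretest in the model, this coefficient is identical whether the dependent variable is the posttest or the gain, so one analysis answers both.
- Do not fill the research question 3 gap with a t-test on the gain scores. At d=0.4 it has less power than the posttest alone when r is below 0.5, and less than pretest adjustment at every r shown.
- Report within-arm changes and gain scores as descriptive means with intervals only.

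Cost: one degree of freedom per model, two variable names, and one or two sentences in the plan. The pretest is already collected and linked, so no new data are needed.
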